- ii). Secure cooperation of clinical bedside nurses and respiratory therapists in administering aerosol.
- iii). Identify and randomize a sufficient number of patients within a reasonable study period. This includes ability to identify eligible infants, obtain informed consent, and prepare and deliver aerosolized study medication in the defined time frame.

1.1.7.3. Dose Finding:

We will randomize infants to receive one of 4 fixed dosing schedules. Data collected during this Phase I/II trial will be critical in selecting the optimal dosing schedule for the definitive Phase III trial. Optimal dosing schedule will be determined by preliminary evidence of efficacy, lack of adverse effects, and tolerance by patients and bedside clinical caregivers.

1.1.7.4. Efficacy:

The primary efficacy outcome for this Phase I/II trial is the need for need for intubation and MV within 72 hours of study intervention (treatment failure). This will be compared to a historical control rate of 0.5 for need for intubation in PT infants 24-36 weeks GA undergoing NIV. Treatment failure criteria are defined *a priori* in Section 3.6.5. We chose treatment failure within 72 hours of randomization as our primary efficacy outcome as failure within that time would likely be due to RDS, whereas failure after this time would more likely be due to secondary causes like sepsis, PDA, pneumonia, NEC, IVH, or apnea of prematurity.

1.1.8. Secondary Efficacy Outcomes:

1. CBG/ABG, pulse oximetry, vital signs at 60±30 minutes after end of AS
2. Number of doses of surfactant – aerosolized & intratracheal
3. Respiratory support at 24, 48 & 72 hours, 7 days (D7), D14, D28, 36 weeks corrected GA and Discharge.
4. Pneumothorax, pneumomediastinum or other air leak
5. Changes in cerebral oxygenation as evaluated by NIRS
6. Changes in surfactant activity in gastric aspirates
7. Cumulative duration of NIV and invasive ventilation on D3, D7, D14, D28, 36 weeks CGA and discharge
8. Duration of supplemental oxygen, intensive care, hospital stay
9. Age at start of feeds, feeding progression, age at full enteral feeds
10. Need for blood transfusions
11. Growth parameters at 7 days, 28 days, 36 weeks corrected GA and discharge
12. Morbidities associated with prematurity: PDA, IVH (Grade III-IV), NEC, periventricular leukomalacia, ventriculomegaly, ROP (stage>3 or requiring treatment), and BPD. Two definitions of BPD will be used:

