Analysis plan to address Aim #2: - Determination of Optimal Dilution and Dosage of AS: The optimum dose is one that produces low toxicity while nearly maximizing the biological response⁸⁹. The optimal dosage will be determined by comparing levels of adverse responses, feasibility items and primary and secondary efficacy treatment outcomes (rates of intubation, diagnosis of PDA, need for blood transfusions, postnatal growth, duration of respiratory support, length of hospital stay, and incidence of complications of prematurity including IVH, sepsis, pneumonia, BPD, NEC, ROP, and death) across the four dosing schedules (Appendix IX, Mock Tables). The optimal dosage/dilution will be the one with the minimum level of adverse responses and highest clinical treatment outcomes.

Analysis plan to address Aim #3 - Short-term efficacy of AS: The primary outcome variable for short-term efficacy is the need for intubation & MV within 72 hours of AS. We will estimate the unconditional probability of benefit for the four dosing schedule groups (I, II, III, IV), the 2 dose groups (100 vs. 200 mg/kg) and the entire study cohort of 120 subjects. We will also compare with reported rates of intubation in historical controls (50%). A special χ^2 test to compare sample proportion with population proportion will be conducted to test the study hypothesis that AS is efficacious. In the comparison analysis, different dosages/dilutions will also be considered as weight using the “optimal” dosage/dilution obtained from Aim #2 as reference. A significantly lower rate of intubation in infants treated with AS in this study as compared to the reported rate of ~0.5 at $p < 0.05$ level (two-sided) will be used as evidence supporting the efficacy of AS. However, it is likely we may not

have power to achieve statistically significant results. Nevertheless these preliminary efficacy data will be crucial in determining outcome measures and effect size for the definitive placebo-controlled Phase III trial.

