A number of secondary outcomes will be assessed using the same methodology. Vital signs, SpO₂, FiO₂, NIV parameters (pressure, rate, flow) and ABG/CBG components (pH, PO₂, PCO₂) will be evaluated before and after study intervention (paired *t*-test) and over time (Longitudinal data analysis). Other secondary outcomes include change in surfactant activity in gastric aspirates, changes in cerebral oxygenation, diagnosis of PDA, need for blood transfusions, postnatal growth, duration of respiratory support, length of hospital stay, and incidence of complications of prematurity including IVH, sepsis, NEC, BPD, pneumonia, ROP, and death. We will describe and compare primary and secondary outcome data overall and by dosing schedule, and in three pre-planned subgroup analyses – by dose regardless of dilution (100 mg/kg vs 200 mg/kg), GA group stratum and nebulizer type, recognizing that we may observe trends of differences between groups without having power to determine statistical significance. We will report dichotomous secondary outcome data as proportions and compare the groups using χ^2 and nonparametric tests. We will report secondary continuous outcome data as mean (SD) for normally distributed data and median (interquartile range [IQR]) for skewed data, and will compare the groups by using parametric (*t*-test, ANOVA) and nonparametric tests (Mann-Whitney U test, Wilcoxon's test) as appropriate. Pairwise group comparisons of the four dosing schedule groups will also be performed, although we may lack power to detect significant differences. In a final posthoc analysis, we will compare infants who received intubation within 72 hours to those who did not to understand risk factors for intubation and their modification by study intervention. This analysis will be presented for the entire group and by dosing schedule group. In *adjusted analyses*, dosing schedule, GA group, nebulizer type, mode of NIV, antenatal steroids, and presence of PDA or IVH will be included as covariates recognizing that these analyses are exploratory and need to be interpreted cautiously. We will consider a p value of <0.05 for statistical significance. Mock tables for the planned analyses are presented in Appendix IX.

Recommendations for statistical analyses by the Data Monitoring Committee (DMC) during the conduct of the trial:

1. Additional factors associated with intubation in enrolled infants – clinical team, time of day/shift, clinical variables (e.g. sepsis, NEC)

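### The scale for growth is not stated: size at discharge mixes growth with length of stay, and an unadjusted comparison at days 7 and 28 forgoes the precision that birth size offers

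*Combined protocol and SAP*

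**What the plan says.** Section 1.1.8, item 11 gives the outcome as "Growth parameters at 7 days, 28 days, 36 weeks corrected GA and discharge". The parameters are not named, and nothing says whether they are analysed as size, gain, velocity or z-score. Items 5 and 6 of the same list (cerebral oxygenation, gastric-aspirate surfactant) are expressly worded as changes. Item 8 makes the duration of hospital stay an outcome in its own right.

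In Section 1.1.12, the Aim #2 plan compares these outcomes, among others, across the four schedules to choose the dosage: "rates of intubation, diagnosis of PDA, need for blood transfusions, postnatal growth, duration of respiratory support, length of hospital stay".

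For continuous secondary outcomes the same section will "compare the groups by using parametric (*t*-test, ANOVA) and nonparametric tests", and adds: "Pairwise group comparisons of the four dosing schedule groups will also be performed". The adjusted model, which the plan calls exploratory, is described thus: "dosing schedule, GA group, nebulizer type, mode of NIV, antenatal steroids, and presence of PDA or IVH will be included as covariates". It has GA group but no birth weight, length or head circumference. Longitudinal analysis is named for vital signs, oxygenation, NIV settings and blood gases, not for growth. No rule covers infants discharged or dead before day 28 or 36 weeks.

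**The concern.** Item 11 mixes two kinds of time point, and each has its own weakness.

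- **Discharge** is not a fixed age. If a schedule speeds recovery, its infants leave sooner and have had fewer days to grow. Compared on size, they look as if they grew less. The bias runs against the better schedule in an outcome used to choose the dosage.
- **Days 7 and 28** are fixed ages, but infants enter at 24 0/7 to 36 6/7 weeks, so early size mostly reflects size at birth. Randomisation keeps the comparison fair. Without the birth measurement, though, the spread in birth size swamps any difference in growth, although the covariate that would remove most of it is routinely recorded.

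Infants discharged before day 28 may also have no day-28 value. Those still measured are then the slower to recover.

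**Working it through.** **The plan's own figures.** There is no SD, effect size or power for growth. The stated 81.8% power with 30 per schedule (Section 1.1.10, Table 13) is for intubation, 0.25 against 0.5. The arcsine formula reproduces it: 2 × (asin√0.5 − asin√0.25) × √30 − 1.96 = 0.5236 × 5.477 − 1.96 = 0.908, and Φ(0.908) = 0.818. It says nothing about growth. All weights, SDs and growth rates below are therefore assumptions.

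**1. Discharge**

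With equal growth, the shift is Δ = rate × days. Five days at 20-30 g/day gives 100-150 g. The standard error is SD × √(2/n), and the chance of a nominally significant lower value (two-sided 0.05) is Φ(Δ/SE − 1.96). Group sizes are those of Table 12: 60 per dose, 30 per schedule. For Δ = 150 g (30 g/day, 5 days):

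| Comparison | Assumed SD | SE | Δ/SE | Probability |
|---|---|---|---|---|
| 60 v 60 | 300 g | 54.8 g | 2.74 | 78% |
| 60 v 60 | 400 g | 73.0 g | 2.05 | 54% |
| 60 v 60 | 500 g | 91.3 g | 1.64 | 38% |
| 60 v 60 | 600 g | 109.5 g | 1.37 | 28% |
| 30 v 30 | 300 g | 77.5 g | 1.94 | 49% |
| 30 v 30 | 400 g | 103.3 g | 1.45 | 31% |

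At 20 g/day (Δ = 100 g), 60 v 60 gives 45% at SD 300 g and 28% at SD 400 g.

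*Does birth size repair this?* A simulation used 30 per schedule, stratum mean birth weights of 900/1450/2200 g (SD 150/250/350 g), mean gain 25 g/day and mean stays of 75/38/16 days. With one schedule discharged 7 days earlier and equal growth rates, the difference was −167 g, nominally significant in 34% of trials. Adjusted for birth weight and GA it was still −167 g. The shift comes from age at measurement, not from omitting birth size.

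**2. Days 7 and 28**

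Assumed for day 7: birth weights of 650, 1050, 1750 and 2650 g at 24, 28, 32 and 36 weeks with 15% CV; day-7 weight 97% of birth weight, with SD 5% of birth weight; 40 infants per GA stratum, split 20 v 20 by dose as in Table 10. Simulated results for 60 v 60:

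| Analysis | SE used by the test | True SD of the difference |
|---|---|---|
| Unadjusted t-test | about 127 g | about 62 g |
| GA strata in the model | about 62 g | about 62 g |
| Birth weight and GA | about 17 g | about 17 g |

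Allocation is stratified by GA, so the true variability of the unadjusted difference is already about 62 g. The t-test does not know this: its false-positive rate is near 0%, and it is conservative. The difference detectable with 80% power is:

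- unadjusted: 1.96 × 127 + 0.84 × 62 = 301 g
- GA strata: 2.80 × 62 = 174 g
- birth weight and GA: 2.80 × 17 = 48 g

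The last figure depends on the 5% scatter. With 10% scatter the SEs with GA strata, and with birth weight and GA, are about 68 and 33 g. With 15% they are about 78 and 49 g. Birth weight still helps.

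Under the weights used for the discharge simulation, birth weight explains about 95% of the variance left within GA strata at day 7 and 87% at day 28. At discharge it explains about 47%.

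**The case against.** **The scale may be appropriate.** Postnatal growth, the term in Section 1.1.12, could mean gain from birth, and the mock tables in Appendix IX are not in the document supplied. This stands in part: a reader may infer that raw size is compared, and that is the natural reading of item 11, but it is not stated. Absolute gain to discharge would not escape the first problem, because gain is rate × stay and shrinks by the same 100-150 g.

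**Stratification already deals with GA.** This largely stands for days 7 and 28. GA group is in the exploratory model and GA stratum is a planned subgroup analysis. On the figures above, GA strata alone remove 1 − (62/127)² = 76% of the nominal variance at day 7. A reader might infer that chance differences in birth size will produce false schedule differences; under stratified allocation the unadjusted t-test errs the other way. What remains is the further fall from about 62 to about 17 g.

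**The consequence is limited.** Aim #2 has no scoring rule, and length of stay sits beside growth in its list, so a schedule that shortens stay is visibly credited. Section 1.1.7.3 bases the choice on efficacy, adverse effects and tolerance, and the plan says that its secondary comparisons may lack power. This lowers the severity. It does not excuse a measure that can point the wrong way, or leaving out an available covariate.

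**The figures are assumed, and the design has changed.** Both are true. Section 1.1.10 moves to 60 infants in each higher stratum with at most 40 in the lowest, and later raises the Phase II total to 220, so equal strata and 60 v 60 are illustrative. More infants would not shrink the discharge shift; they would make it significant more often.

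**Conclusion.** The point holds as two separate matters.

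1. If size (or absolute gain) at discharge is compared, it confounds growth with length of stay. The direction is certain if stay differs between schedules; the size is not. A 5-day difference at 20-30 g/day gives 100-150 g. At 30 g/day this is nominally significant in about 54-78% of 60 v 60 comparisons with SD 400-300 g, 28-38% with SD 600-500 g, and 31-49% at 30 v 30 with SD 400-300 g. That stay will differ by 5 days is itself an assumption.
2. At days 7 and 28 the loss is of precision, not validity: about 127 g unadjusted, 62 g with GA strata and 17 g with birth weight and GA at day 7, under the assumed weights and 5% scatter.

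Three stronger readings are not supported. Omitting birth size does not cause the discharge artefact. The precision loss shown for the fixed ages does not carry over to discharge. Nothing shows that a better schedule would be rejected, since growth is one outcome among many with no stated weight. Severity is minor to moderate.

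**What to change.** - **Define the measures.** Name weight, length and head circumference, and state the scale for each time point.
- **Fixed ages.** Use ANCOVA with the corresponding birth measurement and GA as covariates.
- **Discharge.** Use growth velocity, or change from birth in GA- and sex-specific z-score, and report age at discharge by schedule beside it, because early weight loss makes both measures depend somewhat on length of stay. Do not use raw discharge size in the Aim #2 choice.
- **Missing day-28 values.** Do not substitute a discharge value, which would mix ages again. Report by schedule how many infants had been discharged or had died, and use the serial measurements that are recorded, in a longitudinal model or as velocity.

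The cost is SAP wording and a few extra lines of analysis. Dosing per kg already requires a weight within the first 24 hours, and birth length and head circumference are assumed to be in the routine record. No extra visits or infants are needed.

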**AEROSOLIZED SURVANTA IN NEONATAL RESPIRATORY DISTRESS SYNDROME:
PHASE I/II STUDY (IND 115430)**

NCT02294630

FINAL STUDY PROTOCOL & STATISTICAL ANALYSIS PLAN

Date of last Revision: 07-31-2017

RESEARCH STRATEGY

1.1. Research Design:

1.1.1. Study Design:

This is a proposal for the Phase II portion of our unblinded Phase I/II trial^{1,2}. It is a safety, feasibility and dose finding study of AS for the treatment of RDS in spontaneously breathing PT neonates receiving NIV. To remove selection bias and control temporal trends, infants will be randomized to 4 parallel fixed dosing schedule groups^{1,2}. This Phase II study will identify 1 or 2 optimal doses, and provide additional data for safety, feasibility and early indication of efficacy that will be the basis for designing a definitive Phase III trial. Optimal dose(s) will be identified based on evidence of a significant positive trend with increasing dose, even if no two groups are significantly different^{3,4}. Equitable representation of GAs within each dose group will be achieved by stratified randomization. Equitable representation of two FDA-approved nebulizers will be achieved by using block sizes of 8. It is expected that choice of nebulizer device will not affect efficacy but may influence caregiver preference based on institutional practice and ease of administration (feasibility).

1.1.2. Inclusion Criteria:

1. Infants admitted to the NICU at Hutzel Women's Hospital (HWH)/Children's Hospital of Michigan (CHM)
2. Gestational age of 24^{0/7}-36^{6/7} weeks
3. Postnatal age \leq 24 hours
4. Clinical diagnosis of RDS based on (i) presence of at least two of the four classic symptoms (need of supplemental oxygen, tachypnea, intercostal retractions or grunting), *and* (ii) exclusion of other causes of respiratory failure (Section 3.6.4.1) *and* (iii) Clinician intent to administer surfactant if infant requires intubation
5. Respiratory support with NIV (CPAP or NIPPV or HFNC) with FiO₂ \geq 25% or PEEP \geq 4 cmH₂O or HFNC rate \geq 2 LPM for \leq 8 hours
6. Written informed consent from parent/guardian

1.1.3. Exclusion Criteria:

1. Previous receipt of surfactant
2. Infants with respiratory distress who are unstable and require immediate intubation (Section 3.6.5)
3. Active air leak syndrome (e.g. pneumothorax, pneumomediastinum)
4. Lethal congenital malformations; death anticipated within first 3 days of life; decision to withhold support

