Diagnosis of RDS will be based on⁵ (i) presence of at least two of four classic symptoms (need of supplemental O₂, tachypnea, intercostal retractions or grunting), *and* (ii) exclusion of other causes of respiratory failure, *and* (iii) Clinical team plan to administer surfactant if infant requires intubation. A chest x-ray (CXR) is not mandatory prior to enrollment; however, if obtained clinically, severity of RDS will be graded and results recorded (Appendix VII [Table A4])⁶. We have not mandated a radiologic diagnosis of RDS because classic radiologic findings may evolve over the first 12-24 hours and be modified by early NIV; furthermore, the need for a CXR may unnecessarily delay study intervention^{7,8}.

1.1.4.2. Timing of Aerosolized Surfactant:

Enrolled infants will receive AS at ≤ 24 hours of age & within 8 hours of initiating NIV as several studies have shown that earlier administration of surfactant to PT babies with RDS improves outcomes.

1.1.4.3. Study Intervention – Aerosolized Surfactant Preparation and Dose:

For this study, Survanta (200 mg PL/8 ml) (Beractant, Abbvie Inc.) will be used at two doses – 100 mg/kg and 200 mg/kg and two dilutions (1:1 and 1:2) resulting in 4 dose schedule groups.

Survanta has been chosen as the surfactant for this study as this is the surfactant used exclusively at our institution; it is also the most commonly used surfactant with the longest duration of use in the US^{9,10}. *We will validate aerosolized use of other surfactants in subsequent studies.* Many studies have compared Survanta with other animal derived surfactants, however, consensus regarding the best preparation has yet to be determined¹⁰. Although several relatively small randomized controlled trials (RCTs) showed significant reductions in mortality and need for redosing with high-dose (200 mg/kg) but not low-dose (100 mg/kg) poractant alfa vs. beractant (100 mg/kg)^{11,12}; three large recent retrospective cohort studies of surfactant use in the US (n=51,282 and 14,173) and Australia (n=515) published in 2013 failed to show significant differences in outcome between poractant and beractant in PT neonates with RDS^{9,13,14}. It is speculated that previously described differences in mortality between surfactants may relate to site variation in outcomes⁹.

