Only short binasal prongs will be used for aerosol delivery in the NIV circuit. Since the ventilator circuit for NCPAP and NIPPV is identical, only one type of neonatal nasal prongs (INCA®) will be used. For the HFNC circuit, only the neonatal Fisher & Paykel short binasal prongs will be used. Nasal cannulas will be applied with recommendations that the prong outer diameter occupy $\sim 50\%$ of the nares internal diameter to allow free egress of flow around the cannula³⁴.

d) Number of doses of Aerosolized Surfactant & Intervals between Doses:

Infants will be eligible to receive a 2nd dose of AS 4 hours after the 1st dose of AS if there is continued need for NIV with FiO₂ $\geq 25\%$ or PEEP ≥ 4 cmH₂O or HFNC rate ≥ 2 LPM.

Since most PT infants with RDS receive ≤ 2 doses of intratracheal surfactant as standard of care, we chose 2 doses of AS as being the minimum number to assess efficacy without inordinately delaying standard of care treatment with intratracheal surfactant⁵⁸. Early trials of intratracheal surfactant used dosing intervals ranging from 1 to 12 hours based on ventilator settings. Since pulmonary delivery following aerosolisation is not precisely quantified, we will administer the 2nd dose 4 hours after the 1st if the infant meets criteria.

e) Duration of nebulization:

Time to nebulize each dose will depend upon volume of diluted surfactant, type of nebulizer, and ambient humidity and temperature. It is expected that for each dose nebulization will be <1 hour for the smallest infants and $<4-5$ hours in the largest infants. This Phase II study will provide critical information regarding time for nebulization of various doses for PT babies and will be crucial in determining tolerance of intervention both by the patient and clinical bedside caregivers. This will be one factor in selecting the optimal dose and dilution of AS for the definitive Phase III trial.

1.1.4.5. Gestational Age Group Strata:

Enrolled infants will be stratified by three GA strata (24^{0/7}-28^{6/7}; 29^{0/7} - 32^{6/7}, 33^{0/7} - 36^{6/7}) because need for intubation and MV has been reported to be higher in more immature infants along with higher co-morbidities of prematurity and mortality. Infants <24 weeks will be excluded as most are likely to receive intubation. ^{59,60}

1.1.4.6. Randomization Procedures: Assignment to Surfactant dosing schedule:

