 - a) Physiological definition: receipt of > 30% supplemental oxygen at 36 weeks or the need for positive-pressure support or, in the case of infants requiring < 30% oxygen, the need for any supplemental oxygen at 36 weeks after an attempt at withdrawal of oxygen⁸⁶.
 - b) Receipt of any supplemental oxygen at 36 weeks.
13. Survival to hospital discharge
14. Survival to discharge without severe morbidity, defined as any of the following: BPD, late onset sepsis, ROP, or serious brain abnormality (IVH, periventricular leukomalacia, or ventriculomegaly)

1.1.9. Monitoring for Adverse Events (AEs):

Adverse events (AEs) that will be monitored during the study and a toxicity grading scale for potentially serious and life-threatening AEs is defined in Appendix VII [Tables A8, A9]⁸⁷.

1. Plugging of nasal prongs, increased secretions requiring suctioning, occurrence of coughing/gagging, surfactant reflux from the nose/mouth, residual surfactant in nasal prongs or nebulizer chamber, rainout in ventilator tubing, dislodged prongs, abdominal distension, and agitation
2. Nebulizer malfunction – clogged, no visible mist, disconnected ventilator tubing
3. Bradycardia, tachycardia or hypotension requiring treatment during or within 6 hours after study intervention
4. Desaturations and/or apnea during or within 6 hours after study intervention
5. Need for resuscitation (positive pressure ventilation, chest compression or cardiac medications) during or within 6 hours after intervention
6. Air leak (pneumothorax, pneumomediastinum) during or within 6 hours after study intervention

7. Nasal trauma score (Appendix VII [Table A4]) before AS, at end of AS and 24 hours after end of AS
8. Death

1.1.10. Sample Size:

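### Both BPD definitions are read at 36 weeks with no gestational-age limit, so in infants born late in the 33–36 week stratum acute RDS support can be counted as BPD

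*Combined protocol and SAP*

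**What the plan says.** Section 1.1.8 item 12 lists BPD among the morbidities of prematurity and states "Two definitions of BPD will be used".

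- Definition (a), the physiological one, is met by more than 30% oxygen at 36 weeks, by a need for positive-pressure support, or, at lower oxygen, by "the need for any supplemental oxygen at 36 weeks after an attempt at withdrawal of oxygen".
- Definition (b) is "Receipt of any supplemental oxygen at 36 weeks".

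Neither carries a gestational-age (GA) restriction, a minimum postnatal age, a minimum duration of oxygen, or another time point for later births. Elsewhere (Sections 1.1.4.10 and 1.1.8 item 3) the 36-week time point is given as corrected GA, without a day or window.

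The population runs to 36 6/7 weeks (Section 1.1.2). Inclusion criterion 5 requires non-invasive respiratory support, and Section 1.1.4.2 says "Enrolled infants will receive AS at ≤ 24 hours of age & within 8 hours of initiating NIV". Section 1.1.4.5 says "Enrolled infants will be stratified by three GA strata"; the highest, called Stratum III here, is 33 0/7–36 6/7.

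BPD is then used in three places: item 14, "Survival to discharge without severe morbidity, defined as any of the following: BPD, late onset sepsis, ROP" or serious brain abnormality; the Aim #2 comparison of the four schedules; and the secondary analyses, overall and by GA stratum (Section 1.1.12).

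**The concern.** BPD is meant to capture lung disease that persists well beyond the acute illness. A fixed 36-week reading does that only if the infant has been alive long enough by then. For an infant born shortly before 36 weeks, the reading falls during the acute RDS that brought the infant into the trial, so the outcome can record the entry condition. For an infant born after 36 0/7 there may be no valid reading at all.

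At stake are the BPD rate in Stratum III, any comparison of BPD between strata, the pooled rate, and survival without severe morbidity. BPD is also one of the items weighed in choosing the schedule for Phase III.

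**Working it through.** The plan gives no figure on this point, so there is none to reproduce. The check is date arithmetic.

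**Inputs.** Eligible GA at birth 24 0/7–36 6/7 (Section 1.1.2); strata 24 0/7–28 6/7, 29 0/7–32 6/7 and 33 0/7–36 6/7 (Section 1.1.4.5); assessment at 36 weeks, taken first as 36 0/7 = 252 days.

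**Formula.** Postnatal age at 36 0/7 = 252 − GA at birth in days.

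| Born at | GA in days | Age at 36 0/7 (days) |
|---|---|---|
| 24 0/7 | 168 | 84 |
| 28 6/7 | 202 | 50 |
| 29 0/7 | 203 | 49 |
| 31 6/7 | 223 | 29 |
| 32 0/7 | 224 | 28 |
| 32 6/7 | 230 | 22 |
| 33 0/7 | 231 | 21 |
| 35 0/7 | 245 | 7 |
| 35 6/7 | 251 | 1 |
| 36 0/7 | 252 | 0 |
| 36 6/7 | 258 | −6 |

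The ranges are 50–84 days in Stratum I, 22–49 days in Stratum II, and +21 to −6 days in Stratum III.

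**Can an infant still be on study support at that point?** Yes, on the plan's own timings. Treatment may start up to 24 hours of age, a dose may take up to 4–5 hours in the largest infants, and a second may follow 4 hours after the first (Section 1.1.4.4 d and e). Teams are asked not to change support until the blood gas 60±30 minutes after nebulization ends (Section 1.1.4.10). An infant born at 35 6/7 can be in this sequence at 36 0/7. CPAP or NIPPV then meets definition (a). Supplemental oxygen meets (b), and can meet (a) by level or after an attempted withdrawal.

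**What if 36 weeks means the whole week?** Births at 36 1/7–36 6/7 then fall inside the window instead of after its start, and their acute RDS support can itself qualify. The rule fails under both readings, in different ways.

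**Share of Stratum III.** The stratum spans 258 − 231 + 1 = 28 gestational days. The documents give no distribution of births within it. Assuming an even spread:

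| Status at 36 0/7 | Days of 28 | Share | Of 40 | Of 60 | Of 80 |
|---|---|---|---|---|---|
| Born on or after that date | 7 | 25% | 10 | 15 | 20 |
| At most 3 days old, or not yet born | 10 | 36% | 14 | 21 | 29 |
| At most 7 days old, or not yet born | 14 | 50% | 20 | 30 | 40 |

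Forty is the size in Table 10 and 60 the redistributed target (Section 1.1.10). Eighty assumes that the 40 infants later added to the two higher strata split evenly. The counts are infants exposed to the problem, not infants misclassified.

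**The case against.** The strongest reply is that the consequence is limited. Four parts of it stand.

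- A reader might infer that BPD rates are uninterpretable throughout. They are not: in Strata I and II the reading falls at 22–84 days, and the plan reports by stratum. Within Stratum III an infant born at 33 0/7 still has 21 days for acute disease to resolve, so the trouble is mainly in births from about 35 weeks.
- A reader might infer that the choice of schedule is biased. Randomization is stratified by GA and blocked (Section 1.1.4.6), so each schedule should have a similar share of late births. BPD is also one item among many in Aim #2, and Section 1.1.10 says the trial is not powered for efficacy. The main effect there is noise.
- A reader might infer that every late-born infant meets the definition by being eligible. Criterion 5 can be met by PEEP or cannula flow without FiO₂ of 25% or more, while definition (b) counts oxygen only; positive pressure counts only under (a). The plan gives no expected duration of support by GA, so the number misclassified is unknown.
- It is not certain that some infants are born after the assessment, because the plan does not say which day is meant.

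One further point cannot be settled: the forms and mock tables (Appendices VII–IX) are not in the supplied text, so a restriction there cannot be excluded. But item 12 states both definitions in full and refers to no appendix for a limit.

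None of this supplies the missing limit. Followed as written, the definitions give the wrong label to some late births.

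**Conclusion.** The point holds for Stratum III, chiefly for births from about 35 weeks. There, 36 0/7 comes at 7 days of age or less, and acute support can be recorded as BPD. The Stratum III rate, between-stratum comparisons, the pooled rate and the item 14 composite are distorted, and Aim #2 gains noise. Strata I and II rates remain usable. The primary outcome, intubation and ventilation within 72 hours, is unaffected.

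The age ranges follow from the eligibility and stratum limits alone. The figure of about half of Stratum III rests on the even-births assumption. Table 14 shows a lower percentage needing RDS treatment at 33–36 weeks than at 29–32; if that decline continues within the stratum, the share could be smaller. Because BPD is secondary and the schedules are balanced on GA, this should be corrected but does not threaten the trial's main conclusions.

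**What to change.** In Section 1.1.8 items 12 and 14, and where Section 1.1.12 uses BPD:

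1. Report BPD, under both definitions, only for infants born before 32 0/7 weeks, and state that denominator. The latest such birth, 31 6/7, is 29 days old at 36 0/7, so every infant assessed is past 28 days.
2. For infants born at 32 0/7 or later, report the D28 and discharge respiratory support already recorded as a separate outcome, not labelled physiological BPD.
3. Keep BPD in the item 14 composite only for the earlier-born group. Define the composite without BPD for the others, and show the two versions separately.
4. State which day or window 36 weeks means.

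Do not simply move definition (a) to D28. It depends on an attempt to withdraw oxygen, which is not part of the D28 record. It could not be added afterwards for infants already past that age: accrual goals for the two higher strata were met in December 2016, before the 31 July 2017 revision.

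The cost is analysis wording and table denominators, with no new data collection. BPD gets a smaller denominator, and Stratum II is split at 32 0/7. That cut-off is not in the plan, so its reason (more than 28 days of age at assessment) should be written down with it.
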